### 8.3 Safety Analyses

The proportion of subjects having one or more adverse events (AEs) with new onset or worsening (relative to baseline) between randomization and Day 28 will be presented by actual treatment group. The reporting of AEs will include anticipated observations (AOs), which are specific predefined categories of mild AEs that are potentially associated with the use of non-invasive peripheral nerve stimulation devices such as the study device. A two-sided Fisher's Exact Test will be performed to test the null hypothesis that the true proportions are equal for the two treatments versus the alternative hypothesis that they are not equal. The proportion of subjects reporting new onset or worsening (relative to baseline and/or the period between randomization and Day 28) AEs between Day 28 and Day 56 will be presented for NTX100

treatment. Similar analyses will be done for serious adverse events (SAEs), device-related SAEs, and anticipated observations (AOs).

Adverse events will be coded using the Medical Dictionary for Regulatory Activities (MedDRA). AEs will be summarized at the subject level using counts and percentages by MedDRA system organ class (SOC) and preferred term (PT). AEs will also be summarized at the event level using counts and percentages by SOC/PT and seriousness, by SOC/PT and severity, and by SOC/PT and relationship to the device. AEs will also be summarized at the event level using counts and percentages by Anticipated Observation (AO) code. All AE tables will summarize AEs occurring between randomization and Day 28 separately from AEs occurring between Day 28 and Day 56. AEs reported for each period will be those AEs with new onset or worsening (if present prior to the period) occurring within the period.

Frequency charts of adverse events occurring between randomization and Day 28 and between Day 28 and Day 56 will be produced separately. The proportion of subjects with at least one AE will be presented overall and by SOC. The proportion of subjects with at least one occurrence of individual AEs will be presented for AEs occurring in >3% of subjects overall or within either arm.

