Study Design	The 8 week follow-up duration will consist of two phases: Phase 1 : Randomized Double-Blind Phase lasting 4-wks, during which subjects will be randomized 1:1 into Active or Sham study arms Phase 2 : Open-Label Phase lasting 4-wks, during which all subjects will receive open-label Active treatment			
	Study entry	Screening an Baseline as	d enrollment ssessments	Baseline assessments
	Phase 1: Randomized Double-Blind Phase	1:1 ranc 4-wk Active (blind)	domized 4-wk Sham (blind)	Primery and point accorded to uk 4
	Phase 2: Open-Label Phase	4-wk Active (open-label)	4-wk Active (open-label)	

Maximum Study Duration	The study is estimated to be completed 18 months after the study opens to enrollment.			
Planned enrollment:	Approximately 132 subjects will be randomized (66 per Phase 1 study arm). Subjects who meet eligibility criteria will be randomized (1:1) to Active and Sham arms for Phase 1; randomization will be stratified by site at an allocation of 1:1 for the Active and Sham arms.			
Number of Clinical Sites	4 to 8 clinical sites within the United States.			
Primary Efficacy Endpoint	The primary outcome measure will be responder rate on the CGI-I scale at Week 4 of Phase 1 relative to Baseline and compared between the study arms. Responder rate for the 7-point CGI-I scale will be defined as the proportion of responses of "Much Improved" or "Very Much Improved".			
Key Secondary Efficacy Endpoints	 For all subjects: PGI-I responder rate (defined as for CGI-I) at Week 4 of Phase 1, relative to baseline and compared between study arms. Mean reduction in IRLS score at Week 4 of Phase 1, relative to Baseline and compared between study arms. Mean reduction in MOS-II score at Week 4 of Phase 1, relative to Baseline and compared between study arms. Mean reduction in MOS-II score at Week 4 of Phase 1, relative to Baseline and compared between study arms. Mean reduction in MOS-II score at Week 4 of Phase 1, relative to Baseline and compared between study arms. 			
Safety Endpoint	Descriptive analysis of adverse events for both study arms, classified and tabulated by seriousness, relationship to the device, and severity.			
Additional Study Assessments	 Daily Questionnaire Subject characterization Refractory categorization Medical history Concomitant medications Weekly questionnaire Custom RLS questionnaire Blinding assessment 			

Abbreviations

AE	Adverse Event
AO	Anticipated Observation

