17.3. Safety

17.3.1. Safety Endpoints

The safety endpoint will be a descriptive analysis of adverse events (AEs) for both study arms, classified and tabulated by seriousness, relationship to the device, and severity.

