17.3.2. Safety Analysis

Frequency charts of adverse events occurring at any time during the study will be produced. The proportion of subjects having one or more adverse events between randomization and the Day 28 will be calculated and compared using a comparison of proportions test. The proportion of subjects reporting on or more adverse events at the Day 56 will tabulated. Similar analyses will be done for SAEs and device-related SAEs. Safety analysis will include all subjects who were treated. A Statistical Analysis Plan (SAP) will be developed prior to breaking the blind, which may include additional plans for safety analysis.

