### 3.4 Determination of Sample Size

Sample size estimates were based on data from use of an earlier prototype of this investigational device in a previously approved protocol (RLS-SNS01). Based on these data and assuming a 1:1 allocation to treatment, statistical power of 85%, and a two-sided alpha of 0.05 (or one-sided alpha of 0.025):

- For CGI-I responder rate at Week 4 of Phase 1, the sample size needed is 42 subjects, assuming statistical analysis with a two-proportion normal approximation test.
- For PGI-I responder rate at Week 4 of Phase 1, the sample size needed is 42 subjects, assuming statistical analysis with a two-proportion normal approximation test.
- For reduction in IRLS score at Week 4 of Phase 1, the sample size is 112 subjects, assuming statistical analysis with a two-sample t-test.
- For CGI-I score at Week 4 of Phase 1 relative to Baseline, the sample size needed is 36 subjects, assuming statistical analysis with a two-sample t-test.

The maximum of these sample sizes is 112 subjects. Previous data with this investigational device are not available for the MOS-I or MOS-II. Based on estimates of a 15% dropout rate, approximately 132 subjects will be enrolled in the study to yield approximately 112 completed subjects.

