### 5.0 STATISTICAL CONSIDERATIONS

### 5.1 General Methodology

The statistical analysis of the data obtained from this study will be performed using SAS® version 9.4 or higher.

Data collected in this study will be documented using summary tables, subject data listings, and figures. Continuous variables will be summarized using descriptive statistics, specifically the mean, median, standard deviation, minimum and maximum. Categorical variables will be summarized using frequencies and percentages. For continuous data, the minimum and the maximum will use the same decimal place accuracy as the raw data. The mean, median, and standard deviation will use one more decimal place than the raw data. For categorical data, percentages will be reported to one decimal place. P-values will be reported to 4 decimal places. P-values less than 0.0001 will be displayed as <0.0001 in the tables. All statistical tests for efficacy will be performed at the one-sided 0.025 significance level, and all statistical tests for safety (adverse events) will be performed at the two-sided 0.05 significance level.

Data listings will be sorted by site number and subject ID number.

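### Between-arm safety is planned as Fisher p-values beside counts; adding a risk difference with a 95% interval would show what excess harm is not excluded

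*SAP*

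**What the plan says.** Protocol 17.3.1 sets the status of the endpoint: "The safety endpoint will be a descriptive analysis of adverse events (AEs) for both study arms". Protocol 17.3.2 then asks for the proportion of subjects with at least one AE up to Day 28 to be compared by a test of proportions, and for the same to be done for SAEs and device-related SAEs. It names no interval.

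SAP 8.3 makes the test specific: "A two-sided Fisher's Exact Test will be performed to test the null hypothesis that the true proportions are equal for the two treatments". It extends it: "Similar analyses will be done for serious adverse events (SAEs), device-related SAEs, and anticipated observations (AOs". SAP 5.1 fixes the level: "all statistical tests for safety (adverse events) will be performed at the two-sided 0.05 significance level".

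The Table 3.1 shell has one row block for each of these four outcomes in Phase 1. Each shows n (%) for NTX100, n (%) for sham and a p-value. There is no column for a difference, a ratio or an interval. The only 95% confidence interval specified in the SAP is for the CGI-I responder rate after multiple imputation (SAP 5.3).

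**The concern.** A descriptive safety endpoint should say how large the difference between the arms is and how uncertain it is. Here the only planned inference between the arms is a verdict on equality. The trial was sized on efficacy endpoints, and neither document gives a power figure or a detectable difference for safety.

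For rare outcomes a p-value above 0.05 is therefore likely even when a real excess exists, and it does not show how large an excess remains compatible with the data. In a pivotal sham-controlled trial, a p-value above 0.05 next to a null hypothesis of equal proportions can easily be read as similar safety. An interval would show at once which excess has been excluded and which has not.

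**Working it through.** **Inputs from the documents.** Number per arm: "Approximately 132 subjects will be randomized (66 per Phase 1 study arm". Safety set: "Safety analysis will include all subjects who were treated" (Protocol 17.3.2), so 66 per arm is the planned maximum. Test and level: Fisher, two-sided 0.05 (SAP 8.3 and 5.1). Sizing basis: "statistical power of 85%, and a two-sided alpha of 0.05 (or one-sided alpha of 0.025", applied to efficacy endpoints only.

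**Inputs not in the documents.** No AE rate, no all-cause SAE rate and no relevant increase in harm is given. Protocol 10.1 reports no device-related SAEs in prior studies, without a denominator. All rates below are therefore assumptions, shown as a range.

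**1. The plan's own figure.** SAP 3.4: "Based on estimates of a 15% dropout rate, approximately 132 subjects will be enrolled in the study to yield approximately 112 completed subjects". Check: 112 / (1 − 0.15) = 131.8, rounded up to 132, or 66 per arm. It reproduces.

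**2. Power of the Fisher test.** For true rates p_S (sham) and p_T (NTX100), power = Σ over all pairs (a, b) of Bin(a; 66, p_T) × Bin(b; 66, p_S), counting the pairs whose two-sided Fisher p is at most 0.05. The chance of a miss is 1 − power.

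| Outcome (assumed rates, sham v NTX100) | Power | Miss |
|---|---|---|
| AE 10% v 25% | 55% | 45% |
| AE 20% v 35% | 42% | 58% |
| AE 30% v 45% | 37% | 63% |
| AE 20% v 30% | 20% | 80% |
| AE 20% v 40% | 65% | 35% |
| SAE 0 v 5% | 11% | 89% |
| SAE 1% v 5% | 6% | 94% |
| SAE 0 v 10% | 66% | 34% |

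With 56 per arm (112 / 2) the misses are larger: 43% for AE 20% v 40% and 94% for SAE 0 v 5%.

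**3. SAE count needed for significance when sham has none.** With equal arms, p = 2 × C(66, k) / C(132, k) for k v 0 events. k = 4 gives 0.119, k = 5 gives 0.058 and k = 6 gives 0.028. So 6/66 = 9.1% on NTX100 is needed. The test is also very conservative here: with a true SAE rate of 2% in both arms it rejects about 0.1% of the time, against a nominal 5%.

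**4. What an interval would add.** Newcombe limits for d = p1 − p2, with Wilson limits (l, u) for each arm: lower = d − √[(p1 − l1)² + (u2 − p2)²]; upper = d + √[(u1 − p1)² + (p2 − l2)²].

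- SAEs 5/66 v 0/66: d = 7.6 points, Wilson limits 3.3–16.5% and 0–5.5%. Lower = 7.6 − √(4.3² + 5.5²) = 0.6; upper = 7.6 + √(9.0² + 0²) = 16.5 (unrounded inputs). Fisher p = 0.058.
- SAEs 3/66 v 0/66: d = 4.5 points, interval −1.7 to +12.5, p = 0.24.
- AEs 26/66 v 16/66: d = 15.2 points, interval −0.7 to +30.0, p = 0.092.
- No events in either arm: the interval still reaches +5.5 points. The exact (Clopper-Pearson, two-sided 95%) upper limit for NTX100 alone is 1 − 0.025^(1/66) = 5.4%.

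All of these would print as non-significant in Table 3.1 as drawn, although they leave quite different amounts of excess harm open.

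**The case against.** The other side has several good points.

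- A reader might infer that the SAP turned a descriptive endpoint into significance tests against the protocol. It did not. Protocol 17.3.2 already asks for the comparison for AEs, SAEs and device-related SAEs; the SAP names the test and adds anticipated observations.
- A reader might infer that significant or not significant is all the plan reports between the arms. It is the only inference, not the only result. Table 3.1 gives counts per arm, and Tables 3.2 to 3.6 and the figures give incidence, seriousness, severity and relatedness by treatment. An interval can be computed from these counts by anyone who wants it.
- A reader might infer that the sponsor will treat p > 0.05 as proof of safety. No section says so, and no margin or success rule depends on it. For AEs a significant difference is quite possible, since skin irritation and stimulation discomfort are listed as expected effects in Protocol 9.1 and anticipated observations count as AEs in SAP 8.3.
- Phase 2 adds exposure that a Phase 1 limit ignores: no events in 112 exposed subjects would give an upper limit of 1 − 0.025^(1/112) = 3.2%. That is a one-arm figure, however, and does not replace the sham comparison.

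These points settle the weight of the finding, not its substance. Both arms' counts are there, but the derived figure that a descriptive endpoint most needs is left to the reader, while the less informative p-value is printed.

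**Conclusion.** The point holds as a cheap improvement in reporting. The absence of a risk difference and interval is a fact of SAP 8.3 and the Table 3.1 shell and needs no assumed rate.

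The size of the power problem does rest on assumptions. It is tempting to say that the design misses relevant harm about half the time for AEs and about 90% of the time for SAEs, but the documents do not support this as a property of the trial. Those figures describe a 15-point AE increase from a 10–30% sham rate (45–63%) and SAE increases of 0 v 5% or 1% v 5% (89–94%). Other plausible choices give 35% or 80% for AEs and 34% for SAEs. What can be said without assuming a rate is that, with 66 per arm and no SAEs on sham, six on NTX100 are needed to reach p < 0.05, and that no events in either arm still leaves an excess of about 5 points open. The figures assume 66 treated per arm, with subjects analysed once each for having any event.

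**What to change.** In SAP 8.3 and Table 3.1, for each Phase 1 row (any AE, SAE, device-related SAE, anticipated observation):

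1. Add the NTX100-minus-sham risk difference with a two-sided 95% confidence interval by one named method (for example Miettinen-Nurminen or Newcombe), and make it the main between-arm summary.
2. Where no events occur, give the exact upper limit of the two-sided 95% interval for NTX100.
3. State that any Fisher p-value kept is supplementary, that the interval governs if the two disagree (as they do for 5/66 v 0/66 with Newcombe), and that a non-significant p-value is not evidence of similar safety.

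Protocol 17.3.2 lets the SAP add safety analyses, so these additions do not conflict with it. Dropping the SAE and device-related SAE p-values is optional; because Protocol 17.3.2 specifies those comparisons, dropping them would have to be recorded in SAP 3.5.

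Cost: a few sentences, one table column, and no new data or subjects. The safety statement will look somewhat less favourable, since upper limits of several percentage points will appear even with few or no SAEs.

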### 9.0 OTHER ANALYSES

For subjects assigned to NTX100 in both Phases 1 and 2, frequencies and percentages or descriptive statistics, as appropriate, will be presented for the following variables:

- CGI-I response at Week 8
- PGI-I response at Week 8
- Reduction in IRLS total score from Baseline (Study entry) to Week 8
- Reduction in MOS-II score from Baseline (Study entry) to Week 8
- Reduction in MOS-I score from Baseline (Study entry) to Week 8
- CGI-I score at Week 8

For subjects assigned to Sham in Phase 1 and NTX100 in Phase 2, frequencies and percentages or descriptive statistics, as appropriate, will be presented for the following variables:

- Change in CGI-I responder rate from Week 4 to Week 8 (Week 8 Week 4)
- Change in PGI-I responder rate from Week 4 to Week 8 (Week 8 Week 4)
- Reduction in IRLS total score from Week 4 to Week 8
- Reduction in MOS-II score from Week 4 to Week 8
- Reduction in MOS-I score from Week 4 to Week 8
- Change in CGI-I score from Week 4 to Week 8
- Reduction in IRLS Question #7 score ("How often do you get RLS symptoms?") from Week 4 to Week 8

A blinding assessment will be conducted following Phase 1, in which participants will be asked what treatment they believe they received. The study participants will state their belief regarding their treatment group assignment (i.e., "Treatment", "Sham", or "Don't Know"). A logistic regression analysis will be conducted using data collected at the blinding assessment to assess the blinding. The dependent variable for this analysis will be the participant's guessed treatment, and the explanatory variables will be the participant's actual treatment and the following two PGI-I Day 28 indicator variables: (1) being at least "minimally improved" and (2) being at least "much improved". The PGI-I variables will be used as measures of treatment efficacy. Cases for which the guessed treatment is "Don't Know" or missing will be excluded from the analysis. The estimated coefficient for the actual treatment will be presented, together with the p-value for testing the null hypothesis that the coefficient equals 0 versus the alternative hypothesis that the coefficient does not equal 0. This analysis will be based on the ITT Population. The purpose of the blinding analysis is to evaluate whether there is statistical evidence that the study blinding was compromised. The approach to be taken is to examine whether the actual treatment is predictive of the participant's guessed treatment, after taking into account treatment efficacy.

Further, participants who guess "Treatment" or "Sham" (as opposed to "Don't Know") will be asked for the primary reason for their guess and the results will be summarized by treatment group using frequencies and percentages.

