17.4. Blinding Analysis

A Statistical Analysis Plan (SAP) will be finalized prior to breaking the blind, which will include a plan for blinding analysis. The extent to which subjects remained blinded at the end of Phase 1 will be assessed by calculating a blinding index based on data from the Blinding Assessment following Phase 1, in which subjects will be asked what treatment they believe they received. Further, participants who guess that they received "Treatment" or "Sham" (as opposed to "Don't Know") will be asked for the primary reason for their guess and these results will be analyzed.

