### 3.5 Changes to the Protocol-Specified Analyses

Reduction in IRLS Question #7 score ("How often do you get RLS symptoms?") from Baseline to Week 8 was added as a key secondary efficacy endpoint for subjects assigned to NTX100 in both phases of the study. A summary of the same reduction from Week 4 to Week 8 was added for subjects switching from Sham to NTX100 after Week 4.

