### **5.2** Adjustments for Covariates

There will be no adjustment for covariates in any efficacy or safety analysis, unless there are missing data for the primary efficacy endpoint and multiple imputation methods are used (see Section 5.3). Only the logistic regression analysis conducted to assess the blinding will include adjustment for covariates. The dependent variable for this analysis will be the participant's guessed treatment, and the explanatory variables will be the participant's actual treatment and the following two PGI-I Day 28 indicator variables as covariates: (1) being at least "minimally improved" and (2) being at least "much improved".

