Preferred Term 2	(x:x) xx	(x.xx) xx	xx (xx.x)	xx (xx.x)	xx (xx.x)	xxx (100.0)	×

Creation date, time Program Name: Source: Listing 4

[Programmer's Note: This table will be continued for Sham (Between Randomization and Day 28) and NTX100 (Between Day 28 and Day 56).]

Noctrix Health Inc. Protocol Number: CT-04

Table 3.6

ADVERSE EVENTS (AES): INCIDENCE BY ANTICIPATED OBSERVATION (AO) CODE, AND BY TREATMENT AND TIME PERIOD (EVENT LEVEL)

SAFETY ANALYSIS POPULATION		Sham	(xx=N)	(%) u	(x.x)	xx (xx.x)	xx (xx.x)	xx (xx.x)	(x.xx) xx
SAFETY		NTX100	(xx=N)	(%) u	(x.xx) xx	(xxx)	(xxx)	(xxx) xx	(x.x.x) xx
	Between Randomization and Day 28			AO Code	AO Code 1	AO Code 2	AO Code 3	AO Code 4	AO Code 5

Program Name: Source: Listing 4 Note: Percentages are based on N, the total number of AEs with a non-missing AO code.

Creation date, time

[Programmer's Note: This table will be continued for NTX100 (Between Day 28 and Day 56).]

Table 4

Page x of y

BLINDING ANALYSIS ITT POPULATION

		NTX100	Sham
Variable	Statistic	(N=xx)	(N=xx)
Which device do you think you received for the past 4 weeks? (#1)			
Treatment	u (%) u	xx (xx.x)	xx (xx.x)
Sham	u (%) u	xx (xx.x)	xx (xx.x)
Don't Know	u (%) u	xx (xx.x)	xx (xx.x)
If 'Treatment' or 'Sham' in #1, what was the primary reason for this guess?			
Relief of RLS symptoms	n (%)	xx (xx.x)	xx (xx.x)
Side-effects	u (%) u	xx (xx.x)	xx (xx.x)
Other	n (%)	xx (xx.x)	xx (xx.x)
If 'Treatment' or 'Sham' in #1, Participant's guessed treatment (1)	Coefficient for Actual Treatment	x.x	
	p-value	X.XXXX	

Creation date, time		jistic regression analysis. The dependent variable was the participant's guessed treatment, and the explanatory variables were the participant's actual treatment and the following two PGI-I Day 28	at least 'improved' and (2) being at least 'much improved'. The p-value is from a two-sided test of the null hypothesis that the true coefficient for the actual treatment equals 0 versus the alternative	int does not equal 0.
Program Name:	Source: Listing 5	(1) Results are based on a logistic regression analysis. The dependent var	indicator variables: (1) being at least 'improved' and (2) being at least '	hypothesis that true coefficient does not equal 0.

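### The protocol promises a blinding index; the SAP drops it without saying so and tests the blind only through a PGI-I-adjusted coefficient that has no confidence interval

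*SAP*

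**What the plan says.** Protocol 17.4 fixes the kind of measure: "The extent to which subjects remained blinded at the end of Phase 1 will be assessed by calculating a blinding index". It does not name the index. It leaves the detailed plan to the SAP, which must be final before the blind is broken.

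SAP 9.0 specifies a different analysis: "A logistic regression analysis will be conducted using data collected at the blinding assessment to assess the blinding". Guessed treatment is regressed on actual treatment and two Day 28 PGI-I indicators, at least minimally improved and at least much improved. *Don't Know* and missing guesses are left out. The reason for the covariates is given: "The PGI-I variables will be used as measures of treatment efficacy". The output is limited: "The estimated coefficient for the actual treatment will be presented, together with the p-value for testing the null hypothesis". The aim is stated as "The purpose of the blinding analysis is to evaluate whether there is statistical evidence that the study blinding was compromised". SAP 5.2 confirms the adjustment: "Only the logistic regression analysis conducted to assess the blinding will include adjustment for covariates".

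The Table 4 shell asks "Which device do you think you received for the past 4 weeks" and gives Treatment, Sham and *Don't Know* counts by arm, the main reason for the guess, the coefficient and its p-value. It has no index and no interval.

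SAP 3.5, the section for departures from the protocol's analyses, covers only IRLS Question 7. The Week 8 reduction "was added as a key secondary efficacy endpoint for subjects assigned to NTX100 in both phases of the study", and a matching summary was added for subjects who switch from sham. Blinding is not mentioned.

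**The concern.** A protocol-specified measure has been replaced and the replacement is not declared. What remains answers a narrower question than the protocol asked. The protocol wanted the extent of blinding, and a p-value without an interval does not show extent. A non-significant result could be read as an intact blind.

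The blind matters more than usual here. The primary endpoint and key secondary endpoints 1 to 5 are subjective ratings compared between arms. Under Protocol 16.14 the investigator rates the primary CGI-I after seeing the subject's PGI-I, so a subject's belief has a direct route to the primary endpoint. That same PGI-I is the adjustment variable in the blinding model. It is measured after randomisation, and both real benefit and belief about allocation can move it.

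**Working it through.** **Text comparison.** The documents give no figure for blinding, so there is none to reproduce.

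- Measure: a blinding index in Protocol 17.4; a logistic regression in SAP 9.0 and 5.2.
- *Don't Know*: excluded from the regression, but counted in Table 4.
- Precision: coefficient and p-value only. SAP 5.1 sets test levels for efficacy and safety, so this test has no stated level.
- Declaration: none in SAP 3.5.

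**What adjustment for PGI-I does.** There are three cases.

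1. No efficacy, and belief moves PGI-I. PGI-I then depends on the guess alone. The log odds ratio of guess by arm is about unchanged and its standard error (SE) grows.
2. Real efficacy, and belief moves PGI-I. PGI-I is then a common effect of arm and guess. Conditioning on it pulls the coefficient toward or below zero.
3. Guesses follow felt benefit only. Adjustment then correctly removes that association. This is the SAP's reason for it.

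**Illustrative size.** Sample size comes from Protocol 17.2: 112/(1 - 0.15) = 132 enrolled, 112 completers, 56 per arm. Everything else is assumed: 25% *Don't Know*; 20% of each arm truly know their allocation; the other 55% guess at random; latent PGI-I = N(0,1) + efficacy × arm + d × (guess - 0.5), cut at 0 (minimally improved) and 1 (much improved). There were 2,000 simulated trials per setting, with two-sided tests at 0.05.

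The unadjusted result can be checked by hand:

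- Correct share = 0.20 + 0.55/2 = 0.475; incorrect share = 0.275.
- Log odds ratio = 2 × ln(0.475/0.275) = 1.09.
- Cell counts are 56 × 0.475 = 26.6 and 56 × 0.275 = 15.4, so SE = sqrt(2/26.6 + 2/15.4) = 0.45.
- Power ≈ Φ(1.09/0.45 - 1.96) ≈ 0.68. The simulation gives a coefficient of 1.08-1.14, SE 0.46 and detection of 67-70%.

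SAP model, by belief shift d = 0.5 / 1 / 2 SD:

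| Efficacy | Median coefficient | Detection | Unstable fits |
|---|---|---|---|
| 0 | 1.13 / 1.13 / 1.14 | 65 / 60 / 40% | 1 / 6 / 38% |
| 0.25 SD | 1.05 / 0.94 / 0.73 | 59 / 45 / 19% | 0.4 / 3 / 31% |
| 0.5 SD | 0.94 / 0.71 / 0.32 | 48 / 26 / 7% | 0.3 / 1.3 / 21% |

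At zero efficacy the adjusted SE is 0.48 / 0.52 / 0.67. Unstable means not converged or an SE above 20. Such fits were kept where the variance was finite, so the 2 SD column is rough.

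Other settings:

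- 30% knowing, 0.5 SD efficacy: the SAP model detects 87 / 69 / 27%, against 96-97% unadjusted.
- Belief does not move PGI-I, 20% knowing (800 runs): 65-70% adjusted, against 68-71% unadjusted.
- Nobody unblinded, 0.5 SD efficacy, d = 1 / 2 SD: the adjusted median is -0.43 / -0.87 and the test rejects in 12 / 19% of trials, against 4-5% unadjusted. At d = 0.5 SD it rejects in about 6.5%.
- Guesses follow efficacy only (0.5 or 1.0 SD): the unadjusted test flags 12-70% and the Bang index 7-44% (active) and 10-43% (sham). The SAP model flags 5%.

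**Precision of an index.** For the Bang index by arm (correct minus incorrect share, *Don't Know* kept in the denominator), the 95% half-width is 1.96 × sqrt((0.75 - 0.20²)/56) = 0.22. It is 0.20 with 40% *Don't Know*, 0.24 with 10%, and 0.20 at 66 per arm with 25%.

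**The case against.** The strongest reply has four parts.

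- **Nothing is lost.** Table 4 keeps the guess counts by arm, so an index and an unadjusted odds ratio can be derived from planned output. This is true and limits the severity. But the type of index, the handling of *Don't Know* and the interval would then be chosen after unblinding, which Protocol 17.4 meant to prevent.
- **The protocol left the plan to the SAP and named no index.** This is also true. Any particular index is therefore a suggestion. But the protocol did settle that there would be one, and leaving the detail open does not cover dropping it unannounced.
- **The adjustment is deliberate and works for its purpose.** This stands. When guesses only reflect benefit, the SAP model holds at 5% while the index and the unadjusted test raise false alarms. It is why the adjusted model should stay.
- **The simulated losses need belief to move PGI-I.** The documents give no evidence on this, and both items are collected at Day 28, so either direction is possible. With no such effect the adjustment costs almost nothing, and the largest losses fall in the least stable column. This stands as a limit on the size, but not on the textual gap.

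A coefficient and p-value do imply a rough SE, but Table 4 shows the coefficient to one decimal, so the implied interval is coarse.

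**Conclusion.** The concern holds. The SAP leaves out the index that Protocol 17.4 commits to and does not declare the change. Its only inferential blinding result is a PGI-I-adjusted coefficient without an interval. This part rests on the text alone.

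The practical effect depends on assumptions the documents cannot settle. If belief moves PGI-I by 0.5 to 1 SD and the device has a 0.5 SD effect, the adjusted test finds a 20% compromised blind in 48% to 26% of trials, against roughly 70% unadjusted. If belief has no effect on PGI-I, the two perform alike. Neither analysis replaces the other: the adjusted test can miss a broken blind, and the index or unadjusted coefficient can flag plain efficacy.

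The primary test is not affected. At stake is how firmly the trial can speak about its blind when its endpoints are subjective. This should be corrected, but it does not threaten the trial's validity.

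**What to change.** In SAP 9.0 and Table 4:

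- Add a named blinding index with a 95% confidence interval that counts *Don't Know*, for example Bang by arm.
- Report the actual-treatment coefficient with a 95% confidence interval, both with and without the PGI-I indicators.
- State that the index and the unadjusted coefficient may partly reflect real efficacy, and are to be read beside the adjusted model and the reasons for the guess.

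If the index is not added, declare and explain its removal in SAP 3.5.

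In the same edit, align the name of the first PGI-I indicator. The Table 4 footnote omits the word *minimally*, which SAP 5.2 and 9.0 include. This is clerical.

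The cost is a paragraph and a few table rows, with no new data. The drawback is that a working device can by itself push the index and the unadjusted coefficient away from zero, so the caveat on reading them must be written in.
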